- Vital sign measurements will include weight, temperature, pulse, and resting systolic and diastolic blood pressure. Vital sign measurements of pulse, and systolic and diastolic blood pressure will be collected prior to the infusion of anti-PD-1/PD-L1.
- Physical examination
- ECOG Performance Status
- Clinical laboratory tests (as outlined in the screening phase) (taken and results reviewed prior to study drug administration):
 - Hematology
 - Serum chemistry
 - TSH w/Reflex FT4- week 13 only (for patients who continue pembrolizumab past week 10)
- Blood (optional) for investigational immune response assays at 2 weeks (± 1 weeks) and 8 weeks (± 1 weeks) after completion of radiation therapy.
- Concomitant medications
- Adverse event assessment
- Optional Tumor biopsy

Follow-up

Patients will be seen for an end of treatment visit 3 weeks (± 1 week) after the last pembrolizumab dose and again for follow up visits every 3 months (± 1 month) for 2 years and then every 6 months (± 1 month) for years 3-4 and again at year 5 (± 1 month) per SOC thereafter until progression of disease by imaging criteria or increased symptomatology that requires another therapy. Follow up visits will be performed until 5 years from the last dose of pembrolizumab and will then become optional and SOC.

The following procedures will be performed at each scheduled follow-up visit ± 1 month during the first 2 years. During years 3-5 the clinical laboratory tests will be performed only once per year.

- Measurements of vital signs (resting systolic and diastolic blood pressure, pulse, respiratory rate, and temperature) and weight
- Physical examination
- ECOG Performance Status
- Clinical laboratory tests
 - Hematology
 - Serum chemistry
 - TSH w/Reflex FT4

- Concomitant medications (for the first 2 years)
- Adverse event assessment (for the first 2 years)
- Status of new and continuing AEs and SAEs (at minimum, collected up to 60 days following last dose of pembrolizumab, 6 months for irSAEs definitely related)
- Relevant imaging studies for tumor measurements
- Optional Tumor biopsy

Survival Follow-Up Assessment for all Subjects

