10.1.2.5 Best Overall Confirmed Response

Confirmation of CR and PR for determination of best overall response is required for studies with a primary endpoint that includes response.

Time Point Response First time	Time Point Response Subsequent time point ≥ 4 weeks from first time point	BEST overall confirmed response
C	CR	CR
C	PR	SD, PD or PR*
C R	SD	SD provided minimum criteria for SD duration met, otherwise, PD
C R	PD	SD provided minimum criteria for SD duration met, otherwise, PD
C R	NE	SD provided minimum criteria for SD duration met, otherwise, PD
P	CR	PR
P	PR	PR
P	SD	SD
P R	PD	SD provided minimum criteria for SD duration met, otherwise, PD
P R	NE	SD provided minimum criteria for SD duration met, otherwise, NE
N	NE	NE

*If a CR is *truly* met at first time point, then any disease seen at a subsequent time point, even disease meeting PR criteria relative to baseline, makes the disease PD at that point (since disease must have reappeared after CR). However, sometimes ‘CR’ may be claimed when subsequent scans suggest small lesions were likely still present and in fact the patient had PR or SD, not CR at the first time point. Under these circumstances, the original CR should be changed to PR or SD and the best response is PR or SD. PR as best overall response requires ≥ 4 weeks confirmation.

Patients with a global deterioration of health status requiring discontinuation of treatment or die without objective evidence of disease progression at that time should be reported to be off study treatment due to “symptomatic deterioration.” Every effort should be made to document the objective progression even after discontinuation of

treatment.

10.1.2.6 Duration of Response:

Duration of overall response: The duration of overall response is measured from the time measurement criteria are met for CR or PR (whichever is first recorded) until the first date that recurrent or progressive disease is objectively documented (taking as reference for progressive disease the smallest measurements recorded since the treatment started).

The duration of overall CR is measured from the time measurement criteria are first met for CR until the first date that progressive disease is objectively documented.

Duration of stable disease: Stable disease is measured from the start of the treatment until the criteria for progression are met, taking as reference the smallest measurements recorded since the treatment started, including the baseline measurements.

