10.1.2.8 Progression-Free Survival

Progression-Free Survival (PFS) is defined as the duration of time from study entry to time of progression or death, whichever occurs first.

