12.4 Secondary Analysis

Secondary endpoints: Response rate, overall survival, and duration of response (please see section 10.1).

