12.4.2 Analysis Plan

Data will be summarized using appropriate descriptive statistics: proportions with Wilson's 95% confidence intervals, means, standard deviations, ranges, and Kaplan-Meier estimates for time to event data. The toxicity rates will be monitored continuously and a final count of toxicities will be performed.

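### Duration of response ends only at documented progression, so a responder's death without it is implicitly censored and the Kaplan-Meier curve can only be equal to or higher than a progression-or-death curve

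*Combined protocol and SAP*

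**What the plan says.** Section 10.1.2.6 measures duration of overall response from the first record of CR or PR "until the first date that recurrent or progressive disease is objectively documented". Duration of CR runs "from the time measurement criteria are first met for CR until the first date that progressive disease is objectively documented". Duration of stable disease runs from the start of treatment until the progression criteria are met. None of the three names death.

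Section 10.1.2.8 defines PFS as the "time from study entry to time of progression or death, whichever occurs first".

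Section 12.4 reads "Secondary endpoints: Response rate, overall survival, and duration of response" and points to section 10.1 for the definitions. Section 12.4.2 provides for "Kaplan-Meier estimates for time to event data". Neither section gives a censoring rule for duration of response, a rule for death or new therapy before documented progression, or a competing-risk method.

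Three other places bear on the point:
- Section 10.1.2.5 foresees patients who deteriorate or die without objective progression. It records them as off treatment for symptomatic deterioration and asks that progression still be documented after treatment stops. It does not say what this does to duration of response.
- Section 4 (Follow-up) continues the visits that include imaging "until progression of disease by imaging criteria or increased symptomatology that requires another therapy". Patients then enter survival follow-up, which seeks survival status and date of death.
- Section 2.4 asks for a tumour assessment 3 weeks (± 1 week) after the last dose for all subjects, including those with clinical progression. Section 5.1.1.3 exempts from that visit patients who stop early and are switched to another anti-neoplastic drug.

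**The concern.** A responder who dies without documented progression never meets the end event of 10.1.2.6. Kaplan-Meier has only two ways to treat a patient, as an event or as censored, so the wording implies censoring. Censoring treats the patient as though the response could have continued like that of responders still under observation. For a patient who has died, that is not a meaningful assumption, and if the death was related to the cancer the censoring is likely to be informative.

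PFS, two subsections later, handles the same death as an event. The two endpoints would then treat one patient in opposite ways, and nothing in the plan says this is intended.

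At stake is the reported durability of response in a small single-arm trial. With few responders, the median and the 12-month estimate can turn on one patient.

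**Working it through.** **1. The plan's own figures.** Section 12.5 gives no precision for duration of response. Its only figures concern a proportion. With p = 0.20, n = 30 and z = 1.96, the Wilson centre is (0.20 + 3.8416/60)/(1 + 3.8416/30) = 0.2341. The half-width is (1.96/1.1281) × √(0.16/30 + 3.8416/3600) = 0.1390. The interval is therefore 9.5% to 37.3%, as stated. The half-width is at most 15.5% for up to 8 responders (15.1% at 8, 15.6% at 9), and P(X ≤ 8 | 30, 0.20) = 87.1%, which matches the stated 87%. Both figures reproduce, but neither says anything about duration.

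**2. How many responders.** Section 12.2 expects 20% with PR or CR: 0.20 × 30 = 6. The 56% overall response rate quoted in section 2.2 would give 0.56 × 30 ≈ 17.

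**3. Direction.** At each event time Kaplan-Meier multiplies the curve by (1 − d/r), where d is the number of events and r the number at risk. Changing a death at time u from an event to a censoring at u lowers d at u and leaves r unchanged at every time. Each factor is then equal or larger, so the whole curve is equal or higher. This assumes censoring at the date of death; the plan gives no date.

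**4. One death among six (invented data).** Responses end at 4, 7, 10 and 14 months, and two are ongoing at 20 and 26 months. The month-7 ending is a death without documented progression.

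| Month | Death is an event | Death is censored |
|---|---|---|
| 4 | 5/6 = 0.833 | 5/6 = 0.833 |
| 7 | × 4/5 = 0.667 | 0.833 |
| 10 | × 3/4 = 0.500 | × 3/4 = 0.625 |
| 14 | × 2/3 = 0.333 | × 2/3 = 0.417 |

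The median moves from 10 to 14 months.

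**5. Illustration of size.** Let f be the share of ended responses that end in death without documented progression. The documents do not give f, so it is assumed here to be 5% to 40%. Under constant hazards the censored curve is S(t)^(1−f) and its median is the progression-or-death median divided by (1 − f). Take S(12) = 54% as an anchor; its median is 12 × ln 2 / (−ln 0.54) = 13.5 months.

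| Assumed f | 12-month estimate | Median (months) | Median ratio 1/(1 − f) |
|---|---|---|---|
| 5% | 55.7% | 14.2 | 1.05 |
| 10% | 57.4% | 15.0 | 1.11 |
| 20% | 61.1% | 16.9 | 1.25 |
| 30% | 65.0% | 19.3 | 1.43 |
| 40% | 69.1% | 22.5 | 1.67 |

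With anchors of 40% and 70%, f = 20% gives 48.0% and 75.2%.

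**6. Small samples.** The same model was simulated with 3,000 runs per setting and assumed administrative censoring uniform over 12 to 48 months. With f = 20% and 6 responders, the mean 12-month estimate was 53.9% counting deaths and 60.7% censoring them. With 17 responders it was 54.0% and 61.1%. With 6 responders the 12-month estimate was higher in 41.9% of runs and unchanged in the rest. The censored curve was never lower in any run.

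**The case against.** The plan never states that such patients are censored. It says only that Kaplan-Meier will be used, so the handling is strictly unspecified. That is right, and it limits the claim to what the definition implies. It does not remove the gap, because someone applying 10.1.2.6 as written has no event to enter for a death.

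The plan also tries to obtain the missing scans, through the request in 10.1.2.5 and the post-treatment assessment in 2.4. This matters most for symptom-driven changes of therapy. A reader might infer that every such exit is censored and inflates the duration. The documents do not support that: some of these patients will be scanned. Whether a switch counts as an event, a censoring or neither is also an estimand choice the plan has not made, so there is no stated target against which to call it biased. What stands is that section 4 ends the imaging visits at the switch while 10.1.2.5 still asks for progression to be documented, with no imaging schedule behind the request. Those passages need reconciling. No request for later imaging helps a patient who has died.

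A reader might also take the 96% and 54% duration figures in section 2.2 as the benchmark that an inflated result would mislead against. That goes too far. Section 2.2 also cites response rate, PFS and OS, does not say how the cited trial ended duration of response, and does not call the 54% a Kaplan-Meier rate. No comparison with it is planned.

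Finally, the endpoint is secondary and descriptive, and deaths still appear in overall survival. This lowers the importance but does not justify leaving the definition as it is.

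**Conclusion.** The point holds for deaths. As worded, 10.1.2.6 makes a responder's death without documented progression a non-event, in contrast to PFS, and the implied censoring can only raise the curve or leave it unchanged relative to progression-or-death. This conclusion rests on two things: progression-or-death is the intended target, as it is for PFS, and censoring falls at the date of death.

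The size is unknown and may be zero. With about 6 responders, a single such death can move the median, though it need not.

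It is tempting to quote an inflation of 11%, 25% or 43% in the median (f = 10%, 20%, 30%) as the bias in this trial. The documents do not support that. The share f is assumed, and the constant hazard does not fit the protocol's own background figures: 54% at 12 months would imply √0.54 = 73% at 6 months, against the 96% quoted. If f were widened to include unscanned switches, the percentages would also exceed what adding death alone corrects. They are illustrations only.

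**What to change.** In 10.1.2.6, end duration of response, duration of CR and duration of stable disease at documented progression or death from any cause, whichever is first. Censor patients alive without progression at their last adequate tumour assessment.

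Add one sensitivity analysis that counts symptomatic deterioration, or the start of another anti-cancer therapy before documented progression, as an event. State how the main analysis treats those patients, and reconcile section 4 with 10.1.2.5 on whether imaging is expected after a symptom-driven switch.

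The cost is a sentence or two and one extra analysis. Dates of death are already sought in survival follow-up, and the sample size and the precision statement in 12.5 are unchanged. The reported duration may be slightly shorter. The change is best made before outcome data are examined.

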10.1.2.8 Progression-Free Survival

Progression-Free Survival (PFS) is defined as the duration of time from study entry to time of progression or death, whichever occurs first.

10.1.2.9 Survival

Survival is defined as the duration of time from study entry to time of death or the date of last contact.

10.1.3 irRECIST

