2.4 Study Design and Duration

This is a single institution, single arm, open-label, Phase II treatment study to evaluate the safety and efficacy of palliative radiation therapy combined with pembrolizumab as a means of providing for PD-1/PD-L1 checkpoint blockade in patients with metastatic Merkel Cell Carcinoma as either first line therapy or upon progression on prior therapy.

In this study, pembrolizumab will be administered at 200 mg IV every 3 weeks as standard of care as approved by the FDA. Palliative radiation therapy will be given between the first and second cycles of immunotherapy.

Subject participation in this study comprises the following time periods:

- Screening
 - Screening assesses the subject's eligibility to participate as determined by the inclusion/exclusion criteria.
 - Screening labs and ECOG Performance Status must be completed within 4 weeks of confirmation of eligibility. Imaging must be completed within 4 weeks of confirmation of eligibility and within 6 weeks of starting pembrolizumab therapy.
 - Eligibility must be confirmed within 28 days of signing the informed consent form.

- Pembrolizumab
 - Patients will receive pembrolizumab as a single agent administered 200 mg as standard of care intravenously every 3 weeks until progression or unacceptable toxicity.
 - Laboratory evaluations must be performed and the results examined before administration of each dose.
 - As durable disease stabilization and/or objective tumor response can be seen after early progression before Week 12, it is recommended that, in the absence of dose-limiting toxicities (e.g., serious AEs), immunotherapy be administered over

the initial 12 weeks even in the setting of apparent clinical progression, providing the subject's performance status remains stable.

- All subjects, including those who may have discontinued treatment for drug-related AEs and/or who have evidence of clinical progression, should obtain a tumor assessment 3 weeks (± 1 week) after the last dose of pembrolizumab.

- Based on clinical experience in ongoing and completed immunotherapy studies, the following recommendations apply for subject management in light of the tumor assessment taken 3 weeks (± 1 week) after the last dose of pembrolizumab:

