4. TREATMENT PLAN

Screening/Baseline Visit

The following tests and examinations must be performed and the eligibility criteria satisfied before treatment may begin:

- Histologic diagnosis of Merkel Cell Carcinoma
- Demographics and medical history
- Measurements of weight, height, temperature, pulse, respiratory rate, and resting systolic and diastolic blood pressure
- Complete physical examination
- ECOG Performance Status
- Clinical laboratory tests:
 - Hematology: hemoglobin, hematocrit, CBC counts with differential (including absolute lymphocyte count) and direct platelet count
 - Serum Chemistry: albumin, serum alkaline phosphatase, SGOT (AST)/SGPT (ALT), total bilirubin, calcium, creatinine, glucose, lactate dehydrogenase (LDH), total protein, urea nitrogen (BUN), electrolytes (including sodium, potassium, chloride, and bicarbonate), TSH w/Reflex FT4
 - Urinalysis:
 - Gross examination including specific gravity, protein, glucose, and blood
 - Optional microscopic examination including WBC/HPF, RBC/HPF and any additional findings
- Optional Blood sample obtained for investigational immune response assays
- Chest radiography unless baseline CT scan was performed
- Electrocardiogram
- Relevant baseline radiographic images (e.g. brain, chest, abdomen, pelvis, and bone scans with the exact imaging studies utilized determined by the attending physician) within 6 weeks of initiation of anti-PD-1/PD-L1

- Current medications
- Baseline review of symptoms
- Pregnancy test
- Optional Tumor biopsy

Treatment Visits

The day subjects receive the first dose of pembrolizumab therapy will define Day 1. Subjects are required to have blood collected and chemistry labs analyzed up to 1 week prior to each dose of pembrolizumab. Investigators or an assigned medical professional must review liver function tests from the predosing labs and ensure the results meet dosing requirements prior to authorizing administration of each dose of pembrolizumab.

Subjects will receive a single dose of pembrolizumab as standard of care with 200mg IV every 3 weeks (with a -3 and +7-days window) until disease progression or unacceptable toxicity occurs.

During this treatment phase, the following procedures will be performed within 1 week of each scheduled visit:

- Pregnancy test for WOCBP, required within 6 weeks before first dose of pembrolizumab, then optional as clinically indicated for ongoing doses

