10.1.2.4 Evaluation of Best Overall (unconfirmed) Response

The best overall response is the best time point response recorded from the start of the treatment until disease progression/recurrence (taking as reference for progressive disease the smallest sum recorded since baseline). The patient's best response assignment will depend on the achievement of both measurement and confirmation criteria in some circumstances.

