12.4.1 Analysis Population

All Treated Subjects: All subjects who received at least one dose of pembrolizumab and completed the prescribed course of palliative radiation therapy.

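### Overall survival runs from an undefined study entry but is analysed only in patients who later received a dose and completed radiation, so any gap before dosing counts as guaranteed survival

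*Combined protocol and SAP*

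**What the plan says.** Section 10.1.2.9 defines OS as follows: "Survival is defined as the duration of time from study entry to time of death or the date of last contact". Section 10.1.2.8 gives progression-free survival (PFS) the same start: "Progression-Free Survival (PFS) is defined as the duration of time from study entry to time of progression or death". Neither section, nor any other, ties study entry to a date.

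Other definitions in section 10.1.2 start at treatment. Section 10.1.2.4 says "The best overall response is the best time point response recorded from the start of the treatment until disease progression/recurrence", and section 10.1.2.6 says "Stable disease is measured from the start of the treatment until the criteria for progression are met". Section 4 fixes that date: "The day subjects receive the first dose of pembrolizumab therapy will define Day 1". Nothing equates Day 1 with study entry.

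Section 12.4 lists OS as a secondary endpoint. The set in which it is analysed (12.4.1) is "All subjects who received at least one dose of pembrolizumab and completed the prescribed course of palliative radiation therapy". Section 5.1.2 places radiation between the first and second cycles.

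On timing before the first dose, section 2.4 says "Eligibility must be confirmed within 28 days of signing the informed consent form". It also requires imaging within 4 weeks of eligibility confirmation and within 6 weeks of starting pembrolizumab. Section 4 requires the eligibility criteria to be met before treatment begins, and Appendix 2 requires the eligibility checklist to be complete before registration.

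**The concern.** The problem is the combination of an origin that may lie before the first dose and an analysis set fixed by events after it. A patient who dies or drops out between entry and dosing is removed from the OS analysis. A patient who is kept has that interval counted as survival. The credit is zero or positive for each patient, never negative, so the descriptive OS curve can only move upward.

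The trial has one arm, so no control group shares the shift, and any reader who sets the curve beside outside data carries it into that comparison. An undated origin could also be settled after the data are seen. OS is a named secondary objective, so the definition matters, although no decision in the plan depends on it.

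**Working it through.** **1. The plan's own figures.** The documents give no planning figure for OS. The stated figures concern a response proportion. For 6/30 the Wilson interval has centre (0.20 + 3.84/60)/(1 + 3.84/30) = 0.234 and half-width 1.96·√(0.16/30 + 3.84/3600)/(1 + 3.84/30) = 0.139, which gives [9.5%, 37.3%] as in section 12.5. The half-width is at most 15.5% for 0 to 8 responders (22 or more adds a negligible amount). Under Binomial(30, 0.20) that has probability 0.871, matching the stated 87%. Neither figure involves a time origin.

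**2. Length of the gap before the first dose.** These are the largest gaps that the windows in section 2.4 allow, not expected values.

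| Study entry means | Largest gap to first dose |
|---|---|
| Day 1 | 0 |
| Eligibility confirmation or registration | 42 days (6 weeks), if imaging falls on the day eligibility is confirmed |
| Consent | 28 + 42 = 70 days (10 weeks, 2.3 months) |

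**3. Effect on 12-month OS.** Assume survival from first dose is exponential and passes through the 13.5% 5-year figure in section 2.1.

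- Rate: −ln(0.135)/5 = 0.4005 per year, a median of ln 2/0.4005 = 1.73 years (20.8 months).
- From first dose: S(1) = exp(−0.4005) = 67.0%.
- With a common guaranteed gap g in years: S(1) = exp(−0.4005·(1 − g)).
- Standard error at n=30, ignoring censoring: √(0.67·0.33/30) = 8.6 points.

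| Gap | 12-month OS | Rise (points) | Rise/SE |
|---|---|---|---|
| 0 | 67.0% | 0 | 0 |
| 4 weeks | 69.1% | 2.1 | 0.24 |
| 6 weeks | 70.2% | 3.2 | 0.37 |
| 10 weeks | 72.3% | 5.3 | 0.62 |

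**4. Sensitivity to the curve.** The documents give no OS assumption for this trial, so other medians are assumptions too. For gaps of 42 and 70 days, 12-month OS moves as follows:

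- median 24 months: from 70.7% to 73.6% and 75.6%
- median 12 months: from 50.0% to 54.1% and 57.1%
- median 6 months: from 25.0% to 29.3% and 32.6%

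The largest rise across these is 7.6 points, at the shortest median and the 70-day gap.

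**5. What a Day 1 origin leaves behind.** The set also requires completed radiation, given between cycles 1 and 2. The dosing interval is 21 days with a window of −3/+7 days, so guaranteed time after Day 1 can reach about 21 to 28 days. On the curve in step 3, 12-month OS goes from 67.0% to exp(−0.4005·(1 − 21/365.25)) = 68.6%, or to 69.1% at 28 days. This part is present under every meaning of study entry.

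**The case against.** The strongest reply is that study entry is undefined rather than wrong. The study calendar puts consent and eligibility under a pre-study visit at week 0 and the first dose at week 1, which could suggest that the study starts with dosing. If entry means Day 1, the pre-dose credit is zero. Section 2.4, on the other hand, counts screening as a period of participation. The ambiguity stands, and a reader cannot infer that every analysed patient is certainly credited with pre-treatment survival.

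The ten-week figure is a corner case. It needs entry to mean consent, eligibility to take the full 28 days, imaging on the day eligibility is confirmed, and the whole 6-week imaging window to be used. Nor would the median rise by exactly the gap unless all patients had the same gap. Both limits stand.

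The 13.5% figure is a general stage IV figure, and sections 2.1 and 2.2 expect better survival with checkpoint inhibition. That stands as well. In the scenarios above, better survival gives a smaller rise.

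Different origins for different endpoints are not an error in themselves. Duration of response properly starts when response criteria are first met, and best overall response is a category, not a time. A reader might also take PFS results to be affected, but PFS is defined without appearing among the objectives or the endpoints in section 12.

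The life-expectancy criterion of at least 16 weeks makes early deaths less likely. It does not answer the point, because the gap is added to each retained patient's survival time whether or not anyone dies early.

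**Conclusion.** The point holds in a conditional form. If study entry means consent, eligibility confirmation or registration, sections 10.1.2.9 and 12.4.1 together make the pre-dose interval event-free by construction and shift descriptive OS upward. The gap is 0 if entry means Day 1, at most about 6 weeks for eligibility confirmation or registration, and at most about 10 weeks for consent. On the exponential curve with 13.5% 5-year survival, 12-month OS rises by 0 to about 5 points, under 0.65 SE at n=30. That size rests on an assumed curve and a gap common to all patients; the sensitivity step shows how it changes with the median.

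A reader might infer that the trial's main conclusion is biased. The documents do not support that. The primary response analysis, the futility rule in section 12.2 and the sample size in section 12.5 all rest on response proportions, and OS is a Kaplan-Meier summary with no threshold or test. This is a correction worth making to a secondary endpoint, not a flaw in the design's decision rules.

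**What to change.** In section 10.1.2.9, and in 10.1.2.8 if PFS is to be reported, replace study entry with Day 1 (first dose of pembrolizumab). In section 12.4.1, analyse OS in all patients who received at least one dose.

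If the completed-radiation requirement is kept for OS, start OS at a landmark, the completion of radiation. Changing the origin to Day 1 alone would leave the guaranteed time shown in step 5. A landmark answers a narrower question, survival after completing radiation, and should be labelled so.

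The cost is small: one phrase in each definition and one sentence on the OS population. The first-dose date already defines Day 1, and section 4 already plans survival contact, where possible, for all enrolled subjects. Reported OS becomes slightly less favourable.
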